### 6.3 Definition of Dose-Limiting Toxicity

The dose limiting toxicity period (DLT) will be defined as the time period from the start of nivolumab therapy on C1D15 to the end of cycle 3. DLT will be defined as non-hematologic toxicity of  $\geq$  grade 3 with the exception of grade 3 nausea and vomiting that resolves to  $<$  grade 3 within 72 hours, and infection (infection-related toxicities such as fever/sepsis, see below). The grade 3/4 toxicity, designated to be DLT, should be considered drug-related. Patients with transient grade  $\geq$  3 electrolyte abnormalities that are not clinically significant and are correctable within 24 hours will not be considered a DLT. Patients with  $\geq$  grade 3 transient liver function test abnormalities (AST, ALT, or alkaline phosphatase) that resolve to  $<$  grade 2 within 5 days will not be considered DLT only if it is self-limited without steroid treatment. Grade 3 or 4 infection will not constitute DLT unless it is felt that the infection resulted from unexpectedly complicated myelosuppression (degree or duration).

Hematological DLT will be considered as failure to recover neutrophil count (ANC $\geq$ 500), or platelet count  $\geq$ 25,000, or hemoglobin  $\geq$ 7 by Day 42 in patients with  $<$ 5% blasts in the bone marrow, absence of myelodysplastic changes, and/or absence of evidence of disease by flow cytometry in the bone marrow. For patients with  $\geq$  5% blasts, myelodysplastic changes, or evidence of disease by flow cytometry/cytogenetics, failure to recover neutrophil, platelet count, or hemoglobin may not be considered DLT as this could be the result of persistent disease.

Specifically with nivolumab, any patient who requires high dose steroids (any dose greater than the equivalent to 20 mg prednisone daily) will be considered to have experienced a DLT and will be taken off nivolumab but allowed to remain on decitabine and venetoclax.

Management and dose modifications associated with the above adverse events are outlined in Section 7.

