Liver Function AST, ALT, Bilirubin	Management/Next Dose for Nivolumab
≤ Grade 1	Hold at investigator discretion until ULN or baseline. Resume at same dose level.
Grade 2	Grade 2 (3X UNL to 5X UNL): Hold until grade 1 (UNL-3X UNL) or baseline. Resume at same dose level at investigator discretion.
Grade 3	Grade 3 (5X UNL to 20X UNL) Hold until grade 1 or baseline. Resume at same dose level at investigator discretion with return to grade 1 or baseline within 7 days without steroids. If persistent or steroids are required, off protocol therapy.
Grade 4	Off protocol therapy.

Continued treatment of active immune mediated hepatitis may exacerbate ongoing inflammation.

Holding drug to evaluate liver function test (LFT) changes and early treatment are recommended. LFT changes may occur during steroid tapers from other events and may occur together with other GI events including cholecystitis/pancreatitis.

Please note: Grades for liver function follow UNL rather than multiples of baseline.

Recommended management: see Hepatic AE management algorithm

Diarrhea/ Colitis	Management/Next Dose for Nivolumab
≤ Grade 1	Hold until baseline. No change in dose.
Grade 2	Hold until baseline. No change in dose.
Grade 3	Resume at same dose level at investigator discretion if resolved to grade 1 within 7 days without steroids and no evidence of colitis. If persistent or steroids are required off protocol therapy.
Grade 4	Off protocol therapy.
See GI AE Algorithm for management of symptomatic colitis.	
Patients with Grade 2 symptoms but normal colonoscopy and biopsies may be retreated after resolution.	
Patients who require systemic steroids should be taken off study treatment.	
Please evaluate pituitary function prior to starting steroids if possible without compromising acute care. Evaluation for all patients for additional causes includes C. diff , acute and self-limited infectious and foodborne illness, ischemic bowel, diverticulitis, and IBD.	
Recommended management: see GI AE management Algorithm	

Pancreatitis Amylase/Lipase	Management/Next Dose for Nivolumab
≤ Grade 1	Continue at same dose level if asymptomatic at investigator discretion.
Grade 2	Continue at same dose level if asymptomatic at investigator discretion. If symptomatic, resume at same dose level when resolved

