Prior to starting corticosteroids or hormone replacement for any reason, appropriate

endocrine testing including cortisol, Cortrosyn® adrenocorticotropic hormone (ACTH), thyroid stimulating hormone (TSH), and thyroxine (T4) must be obtained to document baseline.

Please note that in some cases the treatment algorithms recommend steroids if symptoms do not resolve in 7 days. However, this recommendation is not meant to delay steroid treatment at any time it is clinically indicated.

Any patient started on corticosteroids initially, who is determined to not require steroid treatment for an autoimmune AE, may resume therapy after a 2-week observation period without further symptoms at the discretion of the PI or investigator.

Any patient requiring high dose steroids (any dose greater than the equivalent to 20 mg prednisone) will be considered to have experienced a DLT and will be taken off nivolumab. These patients will be allowed to continue receiving decitabine and venetoclax on study.

Patients requiring high dose steroid treatment for autoimmune or inflammatory events should go off study treatment except for a short course of tapering steroids for infusion reaction, skin rash or endocrine events.

Patients with grade 3 thyroiditis and skin rash may continue therapy as for grade 2 events with resolution and stable replacement treatment.

Patients with thyroiditis or hypopituitarism who are stable as above may be restarted with replacement hormones including thyroid hormone and physiologic doses of corticosteroids.

Please note that grading and for hypophysitis with symptoms of headache, visual or neurologic changes or radiologic evidence of pituitary enlargement and other CNS events such as aseptic meningitis or encephalitis should be considered grade 3 events.

Patients may be dose-delayed for evaluation and restarted depending on results.

Any patient started on corticosteroids initially who is determined to not require steroid treatment for an autoimmune adverse event may resume therapy after a 2-week observation period without further symptoms at the discretion of the PI or investigator.

If doses of nivolumab are missed/delayed other than reasons for toxicity, they may be given +2 days of scheduled dose.

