## 7.6 Special circumstances

Given that the average time to respond to decitabine with venetoclax is 1.3 months, it is possible that many patients could achieve a CR or CRI within this time yet also experience a DLT. Patients who achieve a CR or CRI within the this average 1.3 months' time to response, yet also experience a DLT, will be evaluated and treated at the discretion of the PI and sponsor. These patients will not automatically be taken off study, as we do not want to discontinue a study treatment that is providing benefit without determining if the specific DLT is significant enough to

warrant this.

If a patient experiences a DLT attributed to nivolumab requiring the use of high dose steroids ( $\geq 20$  mg prednisone daily, or the equivalent), they will be allowed to continue on study receiving decitabine with venetoclax.

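### Sections 6.3, 7.5 and 7.6 conflict on which drugs a patient who needs high-dose steroids may continue

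*Combined protocol and SAP*

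**What the plan says.** All places are in the combined protocol and SAP.

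- **Section 6.3** makes a need for high-dose steroids, defined as "any dose greater than the equivalent to 20 mg prednisone daily", a DLT. The patient "will be taken off nivolumab but allowed to remain on decitabine and venetoclax".
- **Section 7.5, text after the organ tables,** repeats the rule: "any dose greater than the equivalent to 20 mg prednisone) will be considered to have experienced a DLT and will be taken off nivolumab". It adds: "These patients will be allowed to continue receiving decitabine and venetoclax on study".
- **Section 7.5, the very next paragraph,** says: "Patients requiring high dose steroid treatment for autoimmune or inflammatory events should go off study treatment", and continues "except for a short course of tapering steroids for infusion reaction, skin rash or endocrine events".
- **Section 7.5, organ tables.** The diarrhea/colitis notes say: "Patients who require systemic steroids should be taken off study treatment". For grade 2 pneumonitis a need for steroids takes the patient off study. For grade 2 neurologic events it takes the patient off protocol therapy. The endocrine table, by contrast, lets nivolumab restart at the unchanged dose after a grade 2 or 3 event, once hormone replacement is stable and the patient has been stable off steroids for 2 weeks.
- **Section 7.6** opens its rule with "If a patient experiences a DLT attributed to nivolumab requiring the use of high dose steroids". It puts high dose at 20 mg prednisone daily or more and lets the patient stay on study with decitabine and venetoclax.
- **Section 7.1** glosses study treatment as all three drugs. It also says that when one agent is permanently stopped for toxicity, the other two may be continued.

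**The concern.** Two adjacent paragraphs of 7.5 send the same patient in different directions. One keeps two drugs going; the other, on the meaning given in 7.1, stops all three. An investigator facing an immune-related event on high-dose steroids cannot obey both, and two sites could treat identical patients differently while each followed the protocol.

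The stakes are mainly safety and conduct. The only primary objective (Section 1.1) is safety and the MTD of the combination, and this is the rule for handling the toxicity most specific to the added drug. It decides whether nivolumab may be given again after high-dose steroids and whether the patient receives further decitabine and venetoclax. Further cycles can in turn affect which responses are seen and when progression occurs, although the documents do not allow that effect to be sized.

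**Working it through.** The core of this point is textual, so the check sets the rules side by side.

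| Place | Trigger | Nivolumab | Decitabine and venetoclax |
|---|---|---|---|
| 6.3 | more than 20 mg daily; counts as DLT | stopped | may continue |
| 7.5, first of the two paragraphs | more than 20 mg (daily not stated); counts as DLT | stopped | may continue |
| 7.5, next paragraph | high dose, autoimmune or inflammatory event | stopped, unless short taper for infusion reaction, rash or endocrine event | stopped, if study treatment has its 7.1 meaning; same exception |
| 7.5, colitis | any systemic steroid | stopped | off study treatment; drugs not named |
| 7.5, pneumonitis grade 2 | any steroid | stopped | off study; drugs not named |
| 7.5, neurologic grade 2 | any steroid | stopped | off protocol therapy; drugs not named |
| 7.5, endocrine grade 2 or 3 | steroids given | may restart | not stated |
| 7.6 | 20 mg daily or more, DLT attributed to nivolumab | stopped, by implication | may continue |

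Four patients show where the rows collide.

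1. **Immune-mediated event outside the three exempt kinds, need above 20 mg.** Sections 6.3 and 7.6 and the first 7.5 paragraph allow two drugs to continue. The next paragraph takes the patient off study treatment. These are opposite instructions.
2. **Endocrine event, short taper above 20 mg.** Section 6.3 ends nivolumab without exception. The taper exception lifts the instruction to leave treatment, and the endocrine table allows nivolumab to restart. These are opposite instructions on nivolumab itself.
3. **Colitis, grade 2 pneumonitis or grade 2 neurologic event, steroids at or below 20 mg.** The 6.3 steroid rule is not triggered, yet the organ entry removes the patient. Whether decitabine and venetoclax may continue is not stated.
4. **Need of exactly 20 mg daily.** This is high dose in 7.6 but not in 6.3 or 7.5.

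The plan's computed figures are untouched. Section 9.1 tests 30% against 50% with 13 or more responses in 30. By the exact binomial:

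- P(X ≥ 13 | n = 30, p = 0.30) = 0.0845, against a stated 0.084.
- P(X ≥ 13 | n = 30, p = 0.50) = 0.8192, so the type II error is 1 − 0.8192 = 0.1808, against a stated 0.181.

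Both reproduce, and neither depends on the steroid rule.

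**The case against.** **Study treatment may mean nivolumab only.** Section 7.5 is headed Nivolumab, its tables concern the next nivolumab dose, and 7.1 lets the other two agents continue when one is stopped. Some organ-table entries may well have been meant that way. But the text does not say so, and 7.1 gives the term its three-drug meaning. The narrow reading also leaves patient 2 unresolved, since that conflict concerns nivolumab alone.

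**The second paragraph may be a special case.** It covers autoimmune or inflammatory events, while the first covers any high-dose need. That does not rescue the text. Section 7.6 concerns DLTs attributed to nivolumab, which 7.5 itself says may be immunologic in origin, and it keeps those patients on two drugs.

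**The organ tables are not uniform.** This is correct. The skin, renal and infusion-reaction tables contain no rule removing patients for steroid use, and grade 3 events in the general table are mostly held until steroids are finished. The point is limited to the entries named.

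**A reader might infer that DLT counts depend on which page is followed.** The documents do not support that. Both sentences that declare a steroid-related DLT, in 6.3 and 7.5, say more than 20 mg. The 7.6 wording governs continuation for a patient who already has a DLT. The taper exception attaches to leaving treatment, not to DLT status, so on the plain text a short taper above 20 mg remains a DLT. The choice between stopping one drug and stopping three comes after the DLT is counted, and 9.1 replaces only patients who leave the DLT period for reasons other than DLT.

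**A reader might also size the problem from Section 2.4.3,** which cites grade 2 and grade 3 immune toxicity at 11% each with nivolumab plus azacitidine. That section gives no steroid doses and does not say whether the two groups overlap. Most drug-related non-hematologic grade 3 events are DLTs on grade anyway. Nor does one extra DLT necessarily change a dose decision: 0 of 6 becoming 1 of 6 leaves the level acceptable, and only an existing 1 of 6 becoming 2 of 6 would not.

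**Conclusion.** The conflict is real and stands in the current text. For high-dose steroids given for an autoimmune or inflammatory event outside the three exempt kinds, the protocol both allows and rules out continued decitabine and venetoclax, provided study treatment carries its 7.1 meaning. For exempt tapers above 20 mg, and for endocrine events treated with steroids above 20 mg, it both ends nivolumab and allows it to continue or restart; this holds whatever study treatment means. The organ-specific entries add stricter triggers without saying what happens to the other two drugs.

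The threshold mismatch is secondary, being confined to a need of exactly 20 mg daily.

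The point should be corrected because the safety and continuation instructions cannot all be obeyed. It does not rest on a demonstrated change in the DLT count or in the dose decision, and no estimate of the number of patients affected can be drawn from the documents. An effect on response or PFS is possible but unquantified: patients who received all three drugs stay evaluable for response (6.3.2), and follow-up runs for up to 3 years or until death (6.6).

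**What to change.** Reconcile Section 6.3, Section 7.1, the organ tables and both high-dose paragraphs of Section 7.5, and Section 7.6, so that:

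- one definition of high dose is used throughout, including whether exactly 20 mg qualifies and that the dose is per day;
- the consequence is stated separately for nivolumab, decitabine and venetoclax, in place of terms such as study treatment, study or protocol therapy that leave the drugs unnamed;
- any organ-specific rule meant to override the general one says so;
- the short-taper exception and the endocrine restart rule are squared with the rule that a need above 20 mg ends nivolumab;
- the text confirms that the short-taper exception does not alter DLT status under 6.3, or 6.3 is amended if it is meant to.

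Which threshold and which consequences apply is a clinical decision for the sponsor. The cost is an amendment of wording; the sample size, the 3+3 rules and the 13-of-30 criterion are unaffected.

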# **7. DOSING DELAYS/DOSE MODIFICATIONS**

## **7.1 Dose Delays/Modifications for DLT**

Study treatment (all three drugs) will be held for any patients experiencing a DLT.

Non-hematologic DLT: Patients may restart therapy when the adverse event recovers to CTCAE  $\leq$ grade 1 or to the patient's baseline values. If study treatment is restarted and another non-hematologic DLT is encountered, the patient must be removed from the study.

Hematologic DLT: After the 42 day period and confirmed hematologic DLT: If peripheral blasts are absent AND the bone marrow blasts are less than 5%, then the patient may restart study treatment with decrease of decitabine to 5 days from 10 days of therapy.

If treatment is delayed >6 weeks for an adverse event the patient must be permanently discontinued from study therapy.

Patients requiring > two dose delays for the same event should go off protocol therapy.

Please see specific modifications for Nivolumab (Section 7.3)

Drugs may be resumed per protocol. If a specific agent (e.g. decitabine or nivolumab or venetoclax) is permanently discontinued for toxicity, the other two agents may be continued on study. Decitabine and venetoclax doses should not be reduced following toxicity and dose interruption, they should continue at the same dose as stated in the protocol.

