### **7.1.1 Dose Delays/Modifications for other adverse events**

All three study drugs will be held for adverse events requiring interruption until the toxicity can be evaluated, then resumed unless a drug needs to be permanently discontinued.

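### For a patient on high-dose steroids for an immune event, Section 7.5 gives opposite rules on whether decitabine and venetoclax continue

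*Combined protocol and SAP*

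**What the plan says.** **Rules that keep decitabine and venetoclax**

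- Section 6.3: a patient above 20 mg prednisone equivalent daily "will be considered to have experienced a DLT and will be taken off nivolumab but allowed to remain on decitabine and venetoclax".
- Section 7.6, on a DLT attributed to nivolumab that needs high-dose steroids: "they will be allowed to continue on study receiving decitabine with venetoclax". Here the threshold is at least 20 mg, not greater than 20 mg.
- Section 7.5, the high-dose steroid paragraph after the event tables, repeats the 6.3 rule and adds: "These patients will be allowed to continue receiving decitabine and venetoclax on study".
- Section 7.1 first holds everything ("Study treatment (all three drugs) will be held for any patients experiencing a DLT"), but later says that if one agent "is permanently discontinued for toxicity, the other two agents may be continued on study". Section 7.1.1 is similar for other adverse events: all three drugs are held for evaluation, "then resumed unless a drug needs to be permanently discontinued".

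**Rules that remove the patient**

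- Section 7.5, the very next paragraph: "Patients requiring high dose steroid treatment for autoimmune or inflammatory events should go off study treatment except for a short course of tapering steroids". The exception is for infusion reaction, skin rash or endocrine events.
- Section 7.5, Diarrhea/Colitis table: "Patients who require systemic steroids should be taken off study treatment".
- Section 7.5, Pneumonitis table, grade 2: the patient comes off study if steroids are needed.
- Section 7.5, Liver Function grade 3 and Neurologic events grade 2: the need for steroids takes the patient off protocol therapy. The column heading in these tables refers to the next dose of nivolumab.

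**The concern.** A site treating steroid-requiring colitis, pneumonitis or nephritis above 20 mg cannot follow both paragraphs. Under one, the patient loses nivolumab. Under the other, the patient goes off study treatment, which on its ordinary reading means all three drugs. Section 3.1 admits only patients with no reasonable alternative, so losing decitabine and venetoclax is a serious consequence to leave to a site's choice of paragraph.

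The same paragraphs also disagree about nivolumab itself. The first stops it for any steroid use above the threshold. The second exempts short tapers for three event types, and the endocrine table lets nivolumab resume at the same dose once the patient has been stable off steroids for 2 weeks.

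Section 6.3.2 adds a statistical side. A patient who has received all three drugs is evaluable for response and is not replaced, so inconsistent handling of such patients enters the response count.

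**Working it through.** The plan gives no figure on this point, so the check sets the passages side by side.

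**Step 1. The same patient under each rule (more than 20 mg prednisone equivalent)**

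| Event | 6.3, 7.6 and the first 7.5 paragraph | Second 7.5 paragraph | Event table |
|---|---|---|---|
| Colitis | nivolumab stops, other two continue | off study treatment | off study treatment |
| Pneumonitis, grade 2 | same | off study treatment | off study |
| Liver, grade 3 | same | off study treatment | off protocol therapy |
| Neurologic, grade 2 | same | off study treatment | off protocol therapy |
| Endocrine, grades 2 and 3, short taper | nivolumab stops, other two continue | exempt | nivolumab resumes at same dose |
| Rash or infusion reaction, grade 3, short taper | same | exempt | nivolumab may resume at grade 1 or lower |

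The first four rows conflict on decitabine and venetoclax. The last two conflict on nivolumab.

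**Step 2. Can the text be reconciled?**

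- *Read the second paragraph as a specific exception to the first.* This fails. Section 7.6 addresses exactly the patient whose nivolumab-attributed DLT needs high-dose steroids, and keeps that patient on the other two drugs. Autoimmune or inflammatory events are the usual reason for such steroids, so the exception would swallow most of the rule.
- *Read going off as a temporary hold.* This fails. The tables use hold and off as separate actions.
- *Read study treatment in 7.5 as nivolumab only.* This would remove the conflict between the paragraphs over decitabine and venetoclax. It fits the grade 2 pneumonitis entry poorly, the protocol never states it, and the nivolumab conflict in the last two rows remains.

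**Step 3. Where the direct conflict stops**

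The rules that keep the two drugs apply only to high-dose steroids. At lower doses the tables apply alone, so no two rules collide. The lower-dose lines still need alignment. If the first paragraph governs high doses and the colitis line governs the rest, a patient on a low dose would lose more treatment than one on a high dose.

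**Step 4. How many patients could be affected**

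Section 2.4.3 reports grade 2 and grade 3 immune events at 11% each with nivolumab plus azacitidine. Assume those rates carry over to the 30 patients treated at the MTD:

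- grade 3 only: 0.11 × 30 = 3.3 patients;
- both grades, if in different patients: (0.11 + 0.11) × 30 = 6.6 patients.

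The number facing the decitabine and venetoclax conflict would be smaller. The reported events include rash and hypophysitis, which are of exempt types, and not every event need have required more than 20 mg. The documents give neither the split by type nor the steroid doses, so the range cannot be narrowed.

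**The case against.** The strongest reply is that the intent is clear and the stray text is minor. The rule that stops nivolumab alone appears in three places, and Section 7.1 supports it in general terms. The removal wording sits in a section titled for nivolumab, whose tables concern the next nivolumab dose. The documents also use study treatment and study drug loosely: Section 9.1 at one point equates the study drug with nivolumab. Section 7.5 recommends consulting the PI or drug monitor, and Section 7.6 leaves early responders with a DLT to the PI and sponsor.

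Much of this stands. It makes the liver and neurologic entries ambiguous rather than contradictory, and it shows which rule should win. It does not settle the second paragraph, which lies outside any table, or the colitis and pneumonitis wording. A site should not have to raise a query to learn which of two adjacent paragraphs applies.

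A reader might infer from Section 7.1 that study treatment is formally defined as all three drugs, so that all four tables clearly stop everything. The documents do not support that. The phrase is a parenthesis in a sentence about holding drug for a DLT, and of the four tables only colitis uses the term.

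**Conclusion.** The inconsistency is real and unresolved, within limits. It covers patients above 20 mg prednisone equivalent for an autoimmune or inflammatory event other than infusion reaction, rash or endocrine events. For those three event types, the open question is whether nivolumab may resume after a short taper. The threshold in Section 7.6 also differs from that in 6.3 and 7.5.

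The consequence is mainly for the individual patient. A reader might go further and infer a material loss of power for the 13-of-30 rule. The documents do not support putting a number on that. It would need assumed steroid doses, event types and event timing, and an assumed response rate on the remaining two drugs. It would also have to treat a patient removed early as certain not to respond, although that patient has had induction treatment and marrow is still examined at the end of each induction cycle and at end of treatment. The direction would be toward fewer responders, but the effect is small and depends on assumptions. The stated error rates of the rule, 0.084 and 0.181, reproduce (0.0845 and 0.1808) and are not in question.

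**What to change.** 1. In the second high-dose steroid paragraph of 7.5, replace the instruction to go off study treatment with: *will permanently stop nivolumab; decitabine and venetoclax may continue per 6.3, 7.1 and 7.6*. Align the steroid-triggered lines of the colitis, pneumonitis grade 2, liver grade 3 and neurologic grade 2 entries to the same rule.
2. State in 6.3 and in the first 7.5 paragraph whether the short-taper exception for infusion reaction, rash and endocrine events applies. Say that such an event still counts as a DLT if the dose exceeds 20 mg in the DLT window.
3. Use one threshold throughout 6.3, 7.5 and 7.6.

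Do not redefine every off-therapy instruction in 7.5 as nivolumab only. Leave unchanged the stops that do not depend on steroids: grade 4 events, grade 3 neurologic events, the listed CNS and neuromuscular events, and confirmed myocarditis. Leave unchanged also the stop for immunosuppression beyond steroids. Loosening any of these would be a new clinical safety decision, not a reconciliation.

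The cost is a few sentences and four table lines at the next amendment, with the sponsor's medical agreement on items 1 and 2. It adds no patients, visits or procedures.
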